12.4.2 Data Management and Archiving

The Sponsor will be responsible for the processing and quality control of the data. All source data, eCRFs, copies of protocols and protocol amendments, correspondence, subject identification lists (kept by the Investigator), informed consent forms, and other essential documents must be retained for a period of at least 2 years after the study completion or closure.

No study document or image will be destroyed without prior written agreement between the Sponsor and the Investigator. Should the Investigator wish to assign the study records to another party or move them to another location, advance written notice must be given to the Sponsor.

12.4.3 Direct Access to Source Data/Documentation

The Investigator must maintain, at all times, the primary records, (i.e., the original source of data/source documents) of each subject's data. Examples of source documents are hospital records, office visit records, examining physician's findings or progress notes, consultant's written opinion or notes, laboratory reports, imaging data, and CRFs that are used as the source.

The Investigator may keep a separate subject identification list showing enrollment numbers, names, and dates of birth to allow unambiguous identification of each subject included in the study. It is recommended a note be made in the medical record that the subject is participating in a clinical research study.

The Sponsor, auditors, and health authority inspectors (or their agents) will be given direct access to source data and documentation (e.g., medical chart/records, laboratory test results, images) for source data verification, provided that subject confidentiality is maintained in accordance with local requirements.

13 ETHICS

13.1 INFORMED CONSENT

Written informed consent will be obtained from each subject prior to the subject's medical record or personal health information being shared with any study representative. The subject's willingness to participate in the study will be documented in writing in a study-specific Informed Consent Form, which will be signed and dated by the subject or Legally Authorized Representative. The Investigator will keep the original consent form and a copy will be given to the subject. It will be explained to the subjects that they are free to refuse entry into the study and free to withdraw from the study at any time without prejudice to future treatment. Subjects will be consented for two years or for the duration of the subject's participation in the study.

13.2 INSTITUTIONAL REVIEW BOARD (IRB)

This study must be approved by an appropriate IRB at each registry site. Securing the approval is the responsibility of the Investigator, as defined by ISO 14155-1 and FDA regulations (21 CFR Part 56) prior to enrolling in the study.

The Sponsor must receive a copy of the IRB approval letter (or equivalent documentation) for the study protocol and Informed Consent Form before the site can be activated to enroll patients.

The IRB and Sponsor must approve any significant changes to the protocol, as well as a change of Principal Investigator. Documentation of IRB approval must be provided to the Sponsor. Records of all study review and approval documents must be maintained by the Investigator in the Study File/Regulatory Binder and are subject to inspection by the Sponsor (or designee) or regulatory authority during or after completion of the study.

The Investigator must notify the IRB, as per their reporting guidelines, and the Sponsor when he or she deviates from the protocol (see Section 11.3 above). The Sponsor must be notified of all relevant action taken by the IRB and must receive a copy of all study-related correspondence between the Investigator and the IRB.

The IRB must receive notification of study completion and a final report upon study completion or closure. A copy of these reports must be provided to the Sponsor. The Investigator must maintain an accurate and complete record of all submissions made to the IRB.

13.3 CONFIDENTIALITY REGARDING STUDY SUBJECTS

The Investigator must ensure that the privacy of all subjects, including their personal identity and all personal medical information, will be maintained at all times. In CRFs and other documents or image material submitted to the Sponsor, subjects will not be identified by their names, but by an individual identification code (i.e., subject identification number).

Personal medical information may be reviewed for the purpose of verifying data recorded in the CRFs. A monitor or designee may conduct source-document verification on behalf of the Sponsor, the quality assurance unit, or regulatory authorities. Personal medical information will always be treated as confidential and handled in compliance with the Health Insurance Portability and Accountability Act (HIPAA).

13.4 INDEPENDENT MEDICAL MONITOR

An independent Medical Monitor, an independent physician who is not a participant in the study, will review AEs that occur throughout the course of the study. The activities of the Medical Monitor will be guided by the Safety Plan. The Medical Monitor will be responsible for classifying events by severity, relationship, and seriousness, as well as whether they meet MAE criteria related to the primary safety endpoint. For the Primary Analysis, the Medical Monitor AE assessments will supersede those of the Investigators when there are differences.

13.5 CORE LABORATORY AND IMAGE TRANSFER

A central Core Laboratory will independently evaluate venographic imaging data collected at participating institutions. All protocol-required venograms must be sent to the Core Laboratory for evaluation. Refer to the Core Laboratory Imaging Manual for instructions for submitting data. IVUS images will also be sent to the Core Laboratory for possible future measurements.

13.6 Participating Institutions and Investigators

Study sites and Investigators will be selected based on a variety of factors including, but not limited to, experience with endovascular techniques, access to required facilities and equipment, sufficient and adequately trained personnel, and availability of potential subjects. The criteria used for determination will be documented.

13.7 INVESTIGATOR RESPONSIBILITIES

Investigator responsibilities include, but are not limited to, the following:

- Conducting the study in accordance with this investigational plan, signed agreements, and applicable regulations protecting the rights and safety of study subjects (e.g. IRB reporting requirements)
- Ensuring that informed consent is obtained for each study subject in accordance with the investigational plan
- Ensuring that IRB approval is secured prior to starting the study and ensuring continuing review and approval as required throughout the study
- Ensuring all associates, colleagues, and employees assisting in the conduct of the study are informed about their obligations, are adequately qualified and trained, and meet their commitments
- Maintaining adequate and accurate records and ensuring those records are available for inspection at any time
- Ensuring that conducting the study does not give rise to conflict of interest (financial disclosure is required)

14 ELECTRONIC DATA

Electronic data capture (EDC) will be utilized for data collection in this study. The study EDC will only be accessible to trained, authorized personnel with a unique user identifier and password used to access the system. Passwords will be set to expire periodically. Access to electronic study data will be provided to research personnel upon completion of training. Read and write access will be provided to registry sites but only for information and subject data at their own site. The CRO and Sponsor will have read-only access and can post queries for potential data-related discrepancies. Data will be reviewed, queried, cleaned and locked according to the study-specific Data Management Plan.

15 DEFINITIONS

The following definitions will be used throughout the course of the study:

| Term | Definition | | |
|--|---|--|--|
| Primary Safety Endpoint Definitions | | | |
| Target venous segments (TVS) | The thrombus-containing venous segments, specified by the operator, that were treated with the study device at the index procedure. | | |
| | These segments may include the popliteal vein, caudal femoral vein, cranial femoral vein, profunda/deep femoral vein, common femoral vein, external iliac vein, internal iliac vein, common iliac vein, or the inferior vena cava. | | |
| | This includes segments that were treated with the study device, irrespective of the pre-procedure plan. | | |
| | This does not include segments that were not intentionally treated but were instead passed through to remove the device from the leg | | |
| Primary Analysis population | The first 91 subjects with unilateral acute or subacute DVT of less than or equal to 6 weeks' duration, without recent (≤3 month) history of venous interventions. | | |
| Major adverse event (MAE) | A composite of events through 30 days that include all-cause mortality, major bleeding, new symptomatic PE documented by CTPA, or rethrombosis of a TVS in the Primary Analysis population. | | |
| MAE: All-cause mortality (≤30 days) | Death from any cause, irrespective of relationship to the device or to the procedure. | | |
| MAE: Major bleeding (≤30 days) | Clinically overt bleeding that is associated by a fall in the hemoglobin of ≥ 5 g/dL, transfusion of ≥ 2 units of red blood cells, or involvement of a critical site (e.g. intracranial or intraspinal). | | |
| | Hemoglobinuria is not considered to be clinically-overt and, as such, would in and of itself not constitute major bleeding. | | |
| MAE: New symptomatic pulmonary embolism (PE) | New PE accompanied by symptoms such as dyspnea, chest pain, or other localized symptoms referable to the event. | | |
| (≤30 days) | PE that is present at baseline but does not worsen by evidence with additional emboli confirmed via CTPA does not trigger the MAE definition. | | |
| | New, symptomatic PE documented with CTPA but without a baseline imaging study will trigger the MAE. | | |
| MAE: Target vessel segment (TVS) rethrombosis (≤30 days) | Occlusive thrombosis of a TVS that occurs after patency had previously been restored in the segment, documented by imaging study such as duplex ultrasound, venography, computed tomographic venography, or magnetic resonance venography. | | |
| | Rethrombosis requires imaging documentation of an open TVS at the end of after the index procedure, with imaging documentation of occlusion of the segment thereafter. | | |
| | Rethrombosis can be device-related (for example, from vascular injury caused by the study device), or non device-related (for example, from inadequate anticoagulation). | | |

| Term | Definition | |
|--|---|--|
| Primary Effectiveness Endpoint Definitions | | |
| Technical success | Complete or near complete removal of venous thrombus from the TVS, as determined by the percent reduction in the Marder score for those segments. • When more than one venous segment is treated, the change in Marder score is calculated as the total score for the treated segments prior to intervention with the study device (baseline score) minus the total score after treatment with the study device but before treatment with any adjunctive devices or pharmacologic agents (post-treatment score), divided by the baseline score. | |
| Additional Safety Definition | ns | |
| Adverse event (AE) | An AE is an untoward medical occurrence or exacerbation of an existing medical condition subsequent to treatment with the ClotTriever. | |
| Serious adverse event (SAE) | An adverse event that meets at least one of the following: is fatal; is life-threatening; results in persistent or significant disability/incapacity; results in permanent impairment of a body function or permanent damage to a body structure; results in hospitalization or prolongs a hospitalization; or necessitates medical or surgical intervention to preclude permanent impairment of a body function or permanent damage to a body structure. | |
| Device-related event | An event that can be directly attributed to the use of the device, wherein, if the device functioned 100% to specifications and expectations, the event would not have occurred. Rethrombosis in the absence of device induced vascular trauma (documented on an imaging study or with direct visualization of the vessel) is not device-related; rather it is a complication related to ineffective anticoagulation therapy. Perforation from the study device is device-related, but perforation from a non-study adjunctive device is not. As well, events that occur as a result of downstream venous compression (e.g., May-Thurner syndrome) are not considered device-related. | |
| Procedure-related event | An event that is not device-related and occurs as a result of the procedure. Events that occur ≤30 days of the index procedure or ≤30 days of a secondary procedure performed for a previous procedure-related complication, if the event is not device-related. Examples include complications from ineffective anticoagulation (e.g. rethrombosis), excessive anticoagulation (e.g. bleeding), or vascular access with a non-study device (e.g. generic sheath, guidewire injury); distant complications (e.g. myocardial infarction, pneumonia); or contrast-induced complications (e.g. contrast-induced nephropathy or hypersensitivity reaction). | |
| Reportable adverse event | Reportable AEs include all events considered in the safety analyses, all device- and/or procedure-related AEs, as well as any event resulting in death. | |
| Minor bleeding | Bleeding that does not meet the MAE definition for Major Bleeding. Mild oozing that occurs at an access puncture site and uncomplicated hemoglobinuria are not reported as minor bleeding events. | |

| Term | Definition |
|------------------------------|---|
| Other Definitions | |
| Access site | The venous site used to gain access with the study device at the index procedure. |
| Adjunctive Therapy | Per CLOUT protocol, adjunctive therapy is defined as an additional thrombus removal strategy after ClotTriever thrombectomy has been completed (i.e. balloon, stenting, and placement of IVC filters during ClotTriever procedure session would NOT be considered adjunctive therapy). |
| Deep venous thrombosis (DVT) | Formation of thrombus within a deep vein, exclusive of non-thrombotic external compression or scarring of the wall. |
| Acute (DVT) | Suspected timeframe of the onset of DVT is ≤14 days previously, as determined by the Investigator. |
| Chronic DVT | DVT that, in the Investigator's opinion, began more than 6 weeks previously. |
| Distal DVT | Distal DVT occur in the veins of the calf, most frequently in the posterior tibial and peroneal veins, and less frequently in the anterior tibial and soleal/gastrocnemius veins. |
| Patency | Primary patency means that you perform a procedure to restore patency to a vessel, and report how long patency is maintained without any repeat intervention. Primary-assisted patency defines the durability of an intervention that failed initially but not to the level of thrombosis and was retreated. Secondary patency means that the initial intervention failed to the level of thrombosis and was retreated. Once the second treatment was successfully performed, secondary patency defines the durability of that second intervention. |
| Proximal DVT | Proximal DVT is defined when the process involves the iliac, deep femoral, or popliteal veins. |
| Subacute DVT | DVT that, in the Investigator's opinion, began >14 days but ≤6 weeks previously. |
| Target limb | The limb referable to the TVS. In the case of bilateral treatment, both limbs are target limbs. |

BMI	Body Mass Index, calculated as weight in kg divided by height in m squared
CDT	Catheter Directed Thrombolysis
CEAP	Clinical, Etiologic, Anatomic, Pathophysiologic
CFR	Code of Federal Regulations
CRF	Case Report Form
CRO	Contract Research Organization
CT	ClotTriever
CTPA	Computed Tomography Pulmonary Angiogram
DOAC	Direct Oral Anticoagulant
DVT	Deep Vein Thrombosis
FDA	US Food and Drug Administration
HIPAA	Health Insurance Portability and Accountability Act
ICU	Intensive Care Unit
IFU	Instructions for Use
IRB	Institutional Review Board
ISO	International Organization for Standardization
ITT	Intent-to-Treat
IVC	Inferior Vena Cava
IVUS	Intravascular Ultrasound
LOS	Length of Stay
MAE	Major Adverse Event in the ITT population
MLA	Minimum Lumen Area
MLD	Minimum Lumen Diameter
NPRS	Numerical Pain Rating Scale
PE	Pulmonary Embolism
PHI	Personal Health Information
PMT	Percutaneous Mechanical Thrombectomy
PP	Per Protocol
PTS	Post-Thrombotic Syndrome
RVA	Reference Vessel Area
RVD	Reference Vessel Diameter
rVCSS	Revised Venous Clinical Severity Score
TVS	Target Venous Segment(s)
VKA	Vitamin K Antagonist
VTE	Venous Thromboembolism

1. Description of Study Objectives

The primary objective of this study is to evaluate real world patient outcomes after treatment of acute, subacute, and chronic proximal lower extremity DVT with the ClotTriever Thrombectomy System.

Secondary objectives will consist of the following:

- Assessment of post-thrombotic syndrome, as defined by the Villalta scale¹
- Assessment of symptomatic improvement using the change in venous quality of life indices
- Determination of patency (primary, assisted primary, and secondary)
- Differences in outcome in the acute (≤ 14 days), subacute (>14 days ≤ 6 weeks), and chronic (>6 weeks) cohorts and in other subsets (see Section 5)

2. Study Design

The CLOUD Registry is a prospective, multi-center, observational study of subjects with proximal lower extremity DVT treated with the ClotTriever Thrombectomy System. The Registry will collect data on demographics, comorbidities, details from the DVT diagnosis and treatment, and clinical outcomes through 2-year follow-up.

Up to 500 subjects with proximal lower extremity DVT will be enrolled at up to 50 Registry sites. All subjects who sign consent and are treated with the ClotTriever System will comprise the Full Analysis dataset.

The Primary Analysis datasets are subsets of the approximately 500 subject Full Analysis dataset. Hypothesis testing will be performed on this dataset; the safety endpoint testing will be performed on the Primary Analysis Safety cohort and the effectiveness endpoint testing will be performed on the Primary Analysis Effectiveness Cohort.

- The Primary Analysis Safety cohort will include the first 91 subjects that enroll with a clinical presentation analogous to that used for the literature-derived performance goal (i.e., unilateral acute or subacute DVT of less or equal to 6 weeks' duration). These first 91 subjects will not have been treated with thrombolytic or percutaneous mechanical thrombectomy within the prior 3 months.
- From these same 91 subjects, the Primary Analysis Effectiveness cohort will be the subset of subjects who undergo treatment with the ClotTriever System in venous segments with Core Laboratory determined intraluminal thrombus.

Once the Primary Analysis cohort is fully accrued, subjects meeting these criteria will continue to be enrolled and will be evaluated as part of the Full Analysis dataset.

The primary safety endpoint will be assessed when the 30-day follow-up data on the 91-subject Primary Analysis cohort is complete, allowing evaluation of both the primary safety and effectiveness endpoints. The remainder of the subjects will be enrolled to obtain additional safety and effectiveness data and to

allow subset analyses of various pre-determined subgroups. Subjects in both arms will be followed for 2 years after the index procedure.

2.1. Primary Safety Endpoint

The primary safety endpoint is the rate of Major Adverse Events (MAE). MAEs are defined as a composite endpoint triggered when any of four categories of events through 30 days after the index procedure, as observed in the Primary Analysis Safety Cohort:

- All-cause mortality
- Major bleeding
- New symptomatic PE documented by CTPA
- Rethrombosis of a target venous segment (TVS)

The components of the composite MAE endpoint will be assessed by the independent Medical Monitor.

2.2. Primary Effectiveness Endpoint

The primary effectiveness endpoint is Technical Success, as measured in the Primary Analysis Effectiveness Cohort. Technical Success is defined as complete or near complete ($\geq 75\%$) removal of venous thrombus from the TVS. The endpoint will be determined volumetrically by the percent reduction in the Marder score from baseline (pre-intervention) venogram to the venogram performed after use of the study device but before the use of other adjunctive treatment modalities such as pharmacologic thrombolysis, other mechanical thrombectomy devices, or other intervention with pharmacologic or mechanical means. Adjunctive therapy is defined as an additional thrombus removal strategy after ClotTriever thrombectomy has been completed (i.e. balloon, stenting, and placement of IVC filters during ClotTriever procedure session would NOT be considered adjunctive therapy).

2.3. Secondary Endpoints

The following secondary endpoints will be studied in the Primary Analysis Cohorts:

- Individual components of the MAE composite endpoint through 30 days
- Minor bleeding through 30 days
- Access site complications from the index procedure (hematoma, false aneurysm, perforation) through 30 days
- Device-related death
- Procedure-related death
- At any point during follow-up:
 - TVS patency by duplex ultrasound
 - Rethrombosis of the TVS
 - Device-related rethrombosis of the TVS

- DVT outside of the TVS
- Target limb edema (edema scale of the rVCSS) compared to baseline
- Pain (NPRS) compared to baseline
- EQ-5D, rVCSS, Villalta scores compared to baseline (except discharge)

3. Analysis Populations

3.1. Full Analysis Population

The study will consist of up to 500 subjects, i.e., the Full Analysis dataset, who meet the eligibility criteria and are appropriate candidates for treatment with the ClotTriever Thrombectomy System.

3.2. Primary Analysis Population

The Primary Analysis dataset is a subset of subjects with unilateral acute or subacute DVT of less than or equal to a 6-week duration, without recent (≤ 3 months) venous intervention. The first 91 subjects enrolled who meet these criteria will complete the Primary Analysis dataset. Enrollment of this type of subject will continue once the Primary Analysis cohort is fully accrued, i.e., past the 91 subjects needed for the primary endpoint analyses. These additional subjects will be included in the Full Analysis dataset.

4. Incomplete Date Handling and Missing Data

Incomplete dates will follow the following imputation assignment rules:

1. If day is missing but month and year are present, the day will be set to the first date of the month.
2. If both day and month are missing but year is present, then January 1st will be used as the imputed value.
3. If year is missing, then the date is considered missing. In general, missing data points are not imputed.

Subjects with missing effectiveness data will be assumed to have data missing at random and will be imputed by random selection with replacement of data from subjects with pre- and post-intervention measurement of thrombus removal. By repeating this process, e.g. for 5,000 separate data replicates, an empirical distribution of primary effectiveness endpoint can be derived for an estimated 95% confidence interval based on the quantiles of the empirical distribution. The robustness of the multiple imputation outcome will be tested with a tipping point analysis encompassing all possible imputation outcomes.

5. Statistical Methods and Analysis

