10.5 Missing Data

Every effort will be made to minimize the amount of missing data. Recognizing the difficulty of avoiding some missing data, however, data imputation methods with sensitivity imputation analyses will be specified in the Statistical Analysis Plan. Subjects with missing effectiveness data will be assumed to have missing data at random and will be imputed by random selection with replacement of data from subjects with pre- and post-intervention measurement of thrombus removal. The robustness of the multiple imputation outcome will be tested with a tipping point analysis encompassing all possible imputation outcomes.

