5.1. Sample Size

The performance goal of 34% has been established for the primary safety endpoint, based on a one-sided 97.5% exact binomial test. The 30-day MAE rate is anticipated to be approximately 20%. Under this assumption, the required sample size to achieve a level of 82% power is 86 subjects (**Table 1**).

Assuming 5% attrition over 30 days, enrollment of 91 subjects is necessary for the Primary Analytic Dataset.

Table 1. Sample Size - Primary Safety Endpoint

Measure	
Performance goal	34%
Anticipated freedom from MAE	20%
Significance level	.025
Statistical test	One-sided exact binomial test
Desired power level	82%
Required sample size prior to 5% 30-day attrition rate	86
Required sample size after attrition adjustment	91

A performance goal of 30% has been established for the primary effectiveness endpoint. Anticipating an actual Technical Success rate of approximately 50%, and based upon a one-sided 97.5% exact binomial test, the required sample size to achieve a level of 97% power is 85 subjects (**Table 2**). Since the primary effectiveness endpoint is determined at the time of the index procedure, no attrition has been considered for lost to follow-up or other censoring events. However, the effectiveness endpoint is evaluated in the Primary Analytic Effectiveness cohort, and it is assumed that 3% of enrolled subjects will be treated for DVT in the absence of core laboratory-assessed visible thrombus in the TVS. Assuming a 3% attrition rate for subjects without thrombus, enrollment of 88 subjects will be necessary.

Table 2. Sample Size - Primary Effectiveness Endpoint

Measure	
Performance goal	30%
Anticipated technical success rate	50%
Significance level	.025
Statistical test	One-sided exact binomial test
Desired power level	97%
Required sample size prior to 3% attrition for subjects without thrombus	85
Required sample size after attrition adjustment	88

The required sample size is greater for the primary safety endpoint; 91 vs. 88 subjects. Thus, a total of 91 subjects will be enrolled in the Primary Analysis dataset; providing approximately 91 subjects in the Primary Safety cohort and 88 subjects in the Primary Effectiveness cohort for the primary safety and effectiveness analyses, respectively. The overall power of the study is 80%.

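### The SAP's tipping-point analysis omits the safety endpoint, the only one with planned loss to follow-up, and its partial-date rules can place post-procedure events before the procedure

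*SAP*

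**What the plan says.** **Missing data.** Protocol 10.5 promises that "data imputation methods with sensitivity imputation analyses will be specified in the Statistical Analysis Plan". SAP section 4 begins from a default, "In general, missing data points are not imputed", and makes one exception: "Subjects with missing effectiveness data will be assumed to have data missing at random". Those effectiveness values are resampled from subjects with both measurements, and "The robustness of the multiple imputation outcome will be tested with a tipping point analysis encompassing all possible imputation outcomes". Neither SAP section 4 nor SAP 5.3 gives a rule or a sensitivity analysis for a subject whose 30-day MAE status is unknown.

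**Safety numbers.** SAP 5.1 powers safety on 86 subjects and adds: "Assuming 5% attrition over 30 days, enrollment of 91 subjects is necessary for the Primary Analytic Dataset". The same section closes by describing the 91 enrolled as "providing approximately 91 subjects in the Primary Safety cohort" for the primary safety analysis. For effectiveness, it plans no loss to follow-up, because that endpoint is measured at the procedure.

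**Partial dates.** SAP section 4 has two rules: "If day is missing but month and year are present, the day will be set to the first date of the month" and "If both day and month are missing but year is present, then January 1st will be used as the imputed value". Neither is bounded by the index date.

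**Who decides an MAE.** Protocol 10.2 and SAP 5.3 leave 30-day MAE status to the independent Medical Monitor. Protocol 13.4 says that the Monitor's assessment overrides the investigator's.

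**The concern.** The robustness check sits on the endpoint with no planned follow-up loss and is absent from the one with planned loss. Some unknown 30-day status is foreseeable. Aborted cases are excused from follow-up assessments unless converted to surgery, and are not replaced (Protocol 7.9). Visits are recommended rather than required (Protocol 7.1). The 30-day visit may take place from day 14 (Protocol 7.6). If safety passes by one or two events, the SAP plans nothing to show whether the unobserved subjects could have changed the result.

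SAP 5.1 also leaves some doubt about the denominator, since 86 and about 91 both appear as the safety analysis number. The choice moves the pass limit by one event at the planned attrition.

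The date rules raise a separate, smaller matter. An event known to follow the procedure can receive a date before it. It could then drop out of a 30-day count or give a negative time to event.

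**Working it through.** **Inputs.** From SAP 5.1 and 5.3: goal 34%, read as a ceiling on the MAE rate; exact binomial test, one-sided 0.025; anticipated rate 20%; 86 subjects for 82% power; 5% attrition; 91 enrolled. The planned number unobserved is 91 − 86 = 5. Assumptions of this review: 9 unobserved (about 10%) as a second case; MAE rates of 20% and 40% among the unobserved; uniform dates in step 5.

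**1. The plan's own figure.** The pass limit is the largest c with P(X ≤ c | n, 0.34) ≤ 0.025. For n = 86, c = 20, with P(X ≤ 20 | 86, 0.34) = 0.0209. Power is P(X ≤ 20 | 86, 0.20) = 0.815, against 82% stated. Then 86 / 0.95 = 90.5, rounded up to 91. The sample size reproduces.

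Exact one-sided 97.5% upper limits: 20/86 = 33.6% (pass), 21/86 = 34.9% (fail), 21/91 = 33.1% (pass), 22/91 = 34.3% (fail).

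**2. Effect of the denominator.** Type I error is taken at a true rate of 34%, with missingness unrelated to outcome. Keeping everyone gives a limit of 21 observed MAEs whatever the number unobserved.

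| Unobserved | Completers | Limit, completers | Type I error, completers | Type I error, unobserved kept as event-free | P(verdicts differ), rate 20% |
|---|---|---|---|---|---|
| 2 | 89 | 21 | 0.0226 | 0.0226 | 0 |
| 3 | 88 | 20 | 0.0149 | 0.0266 | 0.067 |
| 5 | 86 | 20 | 0.0209 | 0.0364 | 0.061 |
| 9 | 82 | 19 | 0.0229 | 0.0661 | 0.111 |

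With 5 unobserved, the verdicts differ only at exactly 21 MAEs: P(X = 21 | 86, 0.20) = 0.0605. With 0 or 1 unobserved the limit is also 21 both ways.

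**3. What a safety tipping-point analysis would show, 5 unobserved.** All 91 fail at 22 or more MAEs. A completer pass at x is therefore reversed if the unobserved contribute at least 22 − x events. This is possible only for x = 17 to 20, and P(17 ≤ X ≤ 20 | 86, 0.20) = 0.379.

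The probability of an actual reversal is the sum of P(X = x | 86, 0.20) × P(Y ≥ 22 − x | 5, q) over x = 17 to 20:

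- q = 0.20: 0.1073 × 0.0003 + 0.1028 × 0.0067 + 0.0920 × 0.0579 + 0.0771 × 0.2627 = 0.0263
- q = 0.40: 0.1073 × 0.0102 + 0.1028 × 0.0870 + 0.0920 × 0.3174 + 0.0771 × 0.6630 = 0.0904

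**4. Cost of an ascertained-status denominator.** An MAE that comes to light is always counted, so the subjects dropped may all be MAE-free. In the bounding case every MAE among the 91 is captured and 5 MAE-free subjects are dropped. The limit is then 20, applied to a count from 91. Power is P(X ≤ 20 | 91, 0.20) = 0.732, against P(X ≤ 21 | 91, 0.20) = 0.808 on all 91.

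**5. Dates.** Take 365 equally likely index dates and event days 0 to 30, which gives 365 × 31 = 11,315 combinations. With the day missing, 5,373 events (47.5%) are dated before the procedure. With day and month missing, 10,819 (95.6%) are. Example: a procedure on 20 March and a bleed on 28 March recorded only as March gives 1 March, 19 days before the procedure.

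**The case against.** **Denominator.** The SAP's default is not to impute, and calling an unknown status MAE-free is an imputation. Read with the powering on 86, this points to observed cases, with type I error below 2.5%. The phrase about 91 can be taken as cohort size. This stands. A reader might infer that the plan counts missing subjects as event-free and so inflates type I error; the documents do not support that. What remains is an ambiguity that one sentence would remove.

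**Protocol commitment.** A reader might also infer that the SAP breaks a promise in Protocol 10.5. The opening promise there is general, but the methods it goes on to name are for effectiveness only, and the SAP keeps that scope. The gap is one of good practice, not a breach.

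**Safeguards.** The safety analysis waits for complete 30-day data (SAP section 2), contact attempts are required (Protocol 7.9), MAE components and deaths are reportable (Protocol 9.2), and later visits ask about events since the last one (Protocol 7.6). These should keep the number unobserved small. They do not say what happens to a subject who remains unobserved, and SAP 5.1 itself expects about five.

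**Dates.** It is tempting to say that the date rules corrupt the primary endpoint. They hardly touch it, because the Medical Monitor determines MAE within 30 days. MAE components also normally carry a dated record or image, and a pre-procedure date for an adverse event would be an obvious query. The objection does not cover other date-based endpoints: minor bleeding and access site complications through 30 days, and how long patency lasts.

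**Conclusion.** The point holds in a limited form.

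- The safety endpoint has the only planned follow-up loss and no missing-data sensitivity analysis. At the planned loss of 5, the probability of a completer pass that full follow-up would reverse is 2.6% if the unobserved have a 20% MAE rate and 9.0% at 40%. The 38% chance of landing in the 17 to 20 range says only that a worst case could reverse the pass, not that it is likely to.
- The denominator matters only with three or more unobserved. With 5, it decides the result in 6.1% of trials at a 20% rate, and type I error is 2.1% or 3.6% depending on the reading. The first reading is the more natural one.
- The date rules can give impossible dates, mainly for secondary endpoints. The shares of 47.5% and 95.6% apply only to events with partial dates and rest on uniform dates. The documents do not say how often dates will be partial, so the effect on any count is unknown and probably small.

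This is worth correcting before the data are examined. It does not undermine the design.

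**What to change.** 1. In SAP 5.3, state that the primary safety analysis uses subjects with ascertained 30-day MAE status, say what counts as ascertained, and state that unknown status is not counted as event-free. In SAP 5.1, say about 86 evaluable of 91 enrolled.
2. In SAP section 4, extend the existing tipping-point analysis, including the worst case, to safety subjects without 30-day status. As a sensitivity analysis, apply it also to MAE-free subjects last seen before day 30, since a visit on day 14 leaves the rest of the window unseen.
3. Report the result on all 91 alongside. The denominator in (1) keeps every known MAE and drops only MAE-free unknowns. It is conservative and can lower power, in the bounding case to 73.2% against 80.8%. The SAP should say so.
4. For events known to be post-procedure, set the imputed date no earlier than the index date. State that the Medical Monitor's determination governs 30-day MAE status.

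The cost is a few sentences and one or two tables, plus the possible loss of power in (3). Enrolment, the 91 and the 34% goal are unchanged.
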